4.3.6 Diarrhea

Treat diarrhea promptly with appropriate supportive care, including loperamide. Instruct patients to begin taking loperamide at the first signs of: 1) poorly formed or loose stool, 2) occurrence of more bowel movements than usual in one day, or 3) unusually high volume of stool. Loperamide should be taken in the following manner: 4 mg at first onset of diarrhea, then 2 mg after each unformed stool. Daily dose should not exceed 16 mg/day. Loperamide should not be taken prophylactically. Advise patients to drink plenty of clear fluids to help prevent dehydration caused by diarrhea. Avoid loperamide if there is the presence of blood or mucus in the stool or if diarrhea is accompanied by fever.

4.3.7 Oral Intake and Hydration

Care should be taken to ensure adequate hydration during and after treatment. Popsicles and Gatorade have been found to be useful in this setting.

4.3.8 Anticoagulation prophylaxis

Patient will need to take Lovenox 40 mg subcutaneously daily when patients are getting active treatment with vorinostat and rituxan. Five research participants on this study have developed either pulmonary embolism or deep vein thrombosis. These have been without symptoms and found on CT scans. Lovenox (40 mg) subcutaneously will be taken starting from Cycle 1 Day 1 of study to prevent pulmonary embolus and deep vein thrombosis. Lovenox will continue for at least 28 days status post last dose of vorinostat or rituximab. For patients with creatinine clearance less than 30 ml/min, lovenox dose will be 30 mg subcutaneously daily. Elderly patients with creatinine clearance less than 50 ml/min should also be dosed at 30 mg subcutaneously daily.

4.4 Duration of Therapy

Patients who achieve CR as defined in section 9 will receive two further cycles of VORINOSTAT plus rituximab and then discontinue drug. Radiologic studies will be continued every three months for the first year, and at a minimum of every six months for the next two years. In the absence of treatment delays due to adverse event(s), treatment may continue until one of the following criteria applies:

- Disease progression,
- Intercurrent illness that prevents further administration of treatment,
- Unacceptable adverse event(s),
- Patient decides to withdraw from the study, or
- General or specific changes in the patient's condition render the patient unacceptable for further treatment in the judgment of the investigator.

4.5 Duration of Follow Up

Patients will be followed until disease progression is noted or until death, whichever occurs first. Patients removed from study for unacceptable adverse events will be followed until resolution or stabilization of the adverse event.

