1. OBJECTIVES

- 1.1. To evaluate the anti-tumor activity of VORINOSTAT plus Rituximab as assessed by the objective response rate, time to progression and survival in subjects with indolent lymphoma.
- 1.2. To assess the toxicity profile of VORINOSTAT plus Rituximab in this patient population.

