4.3.5 Radiation Therapy

Patients who require localized external beam radiotherapy at the time of protocol screening should receive it prior to study entry.

Patients who require localized external beam radiotherapy during study will be considered to have progression of lymphoma and will be removed from study.

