- j. After one year of treatment, if the patient achieved two consecutive PR based on prior CT scans or PET, the radiological assessment can be done after every 4 cycles instead of 3 cycles. If patients achieved CR, follow up radiological studies will continue every 3 months for one year, then every six months for the next two years.

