Adverse Events - Adverse events will be monitored by the PMT. Adverse events that do not meet the criteria of serious OR are not unanticipated problems will be reported only in the protocol continuation reports and PMT report (see Table 2 below).

Table 2: City of Hope Adverse Event and Unanticipated Problem Reporting Timelines for the DSMC and IRB

Required Reporting Timelines to DSMC for AE/SAEs
Investigator Initiated Studies

Required Reporting Timeframe to DSMC		
Attribution	UNEXPECTED	EXPECTED
	Death while on active treatment or within 30 days of last day of treatment	
Possibly, Probably, Definitely	5 calendar days	
Unlikely, Unrelated		
	Death after 30 days of last active treatment/therapy	
Possibly, Probably, Definitely	5 calendar days	No reporting required
Unlikely, Unrelated	No reporting required	No reporting required
	Grades 3 and 4 AND meeting the definition of "serious"	
Possibly, Probably, Definitely	5 calendar days	10 calendar days
Unlikely, Unrelated	5 calendar days	10 calendar days
	Grades 1 and 2 AND resulting in "hospitalization"	
Possibly, Probably, Definitely	5 calendar days	10 calendar days
Unlikely, Unrelated	10 calendar days	10 calendar days

Externally Sponsored Studies

Required Reporting Timeframe to DSMC		
Attribution	UNEXPECTED¹	EXPECTED
	Death while on active treatment or within 30 days of last day of treatment	
Possibly, Probably, Definitely	No DSMC reporting required - IRB reporting may be necessary	
Unlikely, Unrelated		
	Death after 30 days of last active treatment/therapy	
Possibly, Probably, Definitely	No DSMC reporting required - IRB reporting may be necessary	
Unlikely, Unrelated		
	Grades 3 and 4 AND meeting the definition of "serious"	
Possibly, Probably, Definitely	No DSMC reporting required - IRB reporting may be necessary	
Unlikely, Unrelated		
	Grades 1 and 2	
Possibly, Probably, Definitely	No DSMC reporting required - IRB reporting may be necessary	

An event determined by the IRB of record to be an Unanticipated Problem (UP) will be communicated to the Investigator and COH DSMC through the COH IRB Operations Director. The DSMC will review the case and make a determination as to whether the study will be suspended, terminated, amended, or allowed to continue without amendment.

Required Reporting Timeframe to IRB of Record		
Attribution	UNEXPECTED	EXPECTED
	Death	
Possibly, Probably, Definitely	5 calendar days	Annual
Unlikely, Unrelated	Annual	Annual
	Grades 3 and 4 AND meeting the definition of a UP	

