9.4.6 Within two weeks of registration, the data manager will complete the On-

Study Form (Form OS).

9.4.7 Within four weeks of completion of each course of treatment, the data manager must complete the following:

- Treatment and Adverse Event Form
- Supplemental Data Form (if applicable)
- Flow Sheets (These are to be submitted along with each treatment form.)

9.4.8 Each time a patient is evaluated for response and/or new follow-up information is obtained the data manager will complete the Response/Off-Study Follow-Up Form.

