10. STATISTICAL CONSIDERATIONS

10.1 Study Design/Endpoints

Response rate (CR+PR) will be the primary endpoint. An underlying 20% response rate will be regarded as not sufficiently active, and the trial is designed to have little chance of missing a 40% response rate. A two-stage design will be used. In the first stage, 17 patients will be enrolled. If 4 or more respond, accrual will continue to a total of 33 patients, with 10 or more responses regarded as evidence of sufficient activity to warrant further investigation. If the true response rate is 20%, the proposed design has a 90% chance of declaring vorinostat plus rituximab insufficiently active, and a 55% chance of stopping early. If the true response rate is 40%, there is a 89% chance of concluding VORINOSTAT is sufficiently active. All patients beginning VORINOSTAT therapy will be included in response rates calculations, which will include exact binomial confidence intervals.

All reportable adverse events will be monitored by the PI and CRA, and reported as described in section 10. Reportable and non-reportable adverse events are routinely tabulated for phase II consortium trials as the reports arrive. The time to progression and overall survival will be estimated using the product-limit method of Kaplan and Meier. Toxicity information recorded will include the type, severity, time of onset, time of resolution, and the probable association with the study regimen. Tables will be constructed to summarize the observed incidence by severity and type of toxicity. Baseline information (e.g. the extent of prior therapy, extent of disease) and demographic information will be presented, as well, to describe the patients treated in this Phase II study.

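### Required follow-up stops at progression, so the overall survival estimate promised in Sections 1.1 and 10.1 would lack most deaths after progression

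*Combined protocol and SAP*

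**What the plan says.** Objective 1.1 sets out to evaluate anti-tumor activity "as assessed by the objective response rate, time to progression and survival in subjects with indolent lymphoma". Section 10.1 states the method: "The time to progression and overall survival will be estimated using the product-limit method of Kaplan and Meier". It gives no start date, event definition or censoring rule for overall survival.

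Section 4.5 ends follow-up earlier than that analysis needs: "Patients will be followed until disease progression is noted or until death, whichever occurs first". It continues: "Patients removed from study for unacceptable adverse events will be followed until resolution or stabilization of the adverse event". Section 4.3.5 adds a further route out: "Patients who require localized external beam radiotherapy during study will be considered to have progression of lymphoma and will be removed from study".

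Some contact could occur after treatment stops. For complete responders, the study calendar says that "follow up radiological studies will continue every 3 months for one year, then every six months for the next two years"; this tracks disease and is not a survival schedule after progression. Section 4.1 lets some complete responders who relapse restart drug. Section 9.4.8 says: "Each time a patient is evaluated for response and/or new follow-up information is obtained the data manager will complete the Response/Off-Study Follow-Up Form". In Table 2 of Section 9.3, the row "Death after 30 days of last active treatment/therapy" requires a report to the monitoring committee only when the death is both unexpected and at least possibly related.

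**The concern.** Overall survival needs vital status for every patient until death or a cut-off date, whether or not the disease has progressed. Section 4.5 releases patients at progression, so later deaths, and the dates on which surviving progressors were last known alive, fall outside required follow-up.

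The analyst would then have three poor choices:

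- Censor progressors at progression. This is informative censoring whenever the death hazard changes at progression. If the hazard rises, survival is overstated.
- Count progression as an event. The result is progression-free survival, not overall survival.
- Use whatever later information happens to arrive. If deaths come to light while surviving progressors stay censored at progression, the bias can go either way.

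The second sentence of Section 4.5 adds an ambiguity. It can mean extra adverse-event follow-up, or it can mean that progression follow-up may stop for patients removed for toxicity. The second reading would affect time to progression too.

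**Working it through.** **1. The plan's own figures.** The only operating characteristics given are for the response design in Section 10.1: 17 patients, continue with 4 or more responses, then 33 patients, success with 10 or more. Exact binomial calculation:

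- Early stopping at a 20% response rate: 1 − P(X₁ ≥ 4) = 54.9% (stated 55%).
- Success probability: the sum over x₁ ≥ 4 of P(X₁ = x₁) × P(X₂ ≥ 10 − x₁), with X₂ from 16 patients. At 20% it is 9.9%, so 90.1% declared inactive (stated 90%). At 40% it is 88.8% (stated 89%).

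These reproduce, and survival does not enter them.

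**2. Is survival followed anywhere else?**

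| Place | What it provides | Finds deaths after progression systematically? |
|---|---|---|
| 4.5 | Follow-up to progression or death | No |
| Study calendar | Off-study evaluation; up to three years of imaging for complete responders | No |
| 4.1 | Possible re-treatment of some relapsed complete responders | Only while they are seen |
| 9.4.8 | A form completed when information is obtained | No contact scheduled |
| 9.1 and 9.3 | Reporting of events that become known | No |
| 10.5.1 | Early death as a response category | No |

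**3. Illustrative size.** All rates here are assumptions. Times are exponential, in months:

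- λ = ln 2 / median time to progression (12 or 24)
- h = monthly hazard of death without progression (0.002 or 0.005)
- μ = ln 2 / median post-progression survival (24 or 36; milder cases 60 and 96)
- t = 36, with no other censoring

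Formulas:

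- True OS(t) = e^(−(λ+h)t) + [λ/(λ+h−μ)] × [e^(−μt) − e^(−(λ+h)t)]
- Kaplan-Meier with censoring at progression = e^(−ht)
- Deaths seen, as a proportion of patients = [h/(λ+h)] × [1 − e^(−(λ+h)t)]

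One case in full (medians 12 and 24, h = 0.002): λ = 0.0578, μ = 0.0289.

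- True OS = 0.1163 + 0.4437 = 56.0%.
- Kaplan-Meier = e^(−0.072) = 93.1%.
- Deaths seen = 0.0296 of patients, out of 1 − 0.560 = 0.440 dying: 6.7%.
- Expected deaths outside follow-up in 33 patients = 33 × (0.440 − 0.0296) = 13.5.

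| Median TTP | h | Median post-progression survival | True 3-year OS, % | Censored at progression, % | Deaths seen, % |
|---|---|---|---|---|---|
| 12 | 0.002 | 24 | 56.0 | 93.1 | 6.7 |
| 12 | 0.002 | 36 | 66.3 | 93.1 | 8.8 |
| 12 | 0.005 | 24 | 52.9 | 83.5 | 15.2 |
| 12 | 0.005 | 36 | 63.0 | 83.5 | 19.3 |
| 24 | 0.002 | 24 | 68.4 | 93.1 | 13.7 |
| 24 | 0.002 | 36 | 75.4 | 93.1 | 17.6 |
| 24 | 0.005 | 24 | 63.2 | 83.5 | 28.2 |
| 24 | 0.005 | 36 | 69.9 | 83.5 | 34.6 |
| 12 | 0.002 | 96 | 83.6 | 93.1 | 18.1 |
| 12 | 0.005 | 96 | 79.8 | 83.5 | 35.3 |
| 24 | 0.002 | 96 | 86.9 | 93.1 | 33.1 |
| 24 | 0.005 | 96 | 81.1 | 83.5 | 54.9 |

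Over the first eight rows the excess is 13.6-37.0 points, with 6.5-13.5 expected deaths outside follow-up in 33 patients. At a 60-month post-progression median it is 6.9-16.3 points. At 96 months it is 2.5-9.4 points, with 2.8-4.4 deaths outside follow-up.

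**4. Other horizons.** The documents name none. With 24-36 months post-progression survival, the excess is 2.4-7.9 points at 12 months and 7.5-22.5 at 24 months. With 96 months it is 0.4-1.7 and 1.3-5.2.

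**5. A second set of assumptions.** A simulation with median time to progression of 12-30 months, and death at 1-3% per year before progression and 10-30% per year after, gives true 3-year survival of about 59-89%, against 91-97% when censored at progression. The excess is about 6-36 points.

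**The case against.** The best defence is that deaths may reach the trial by other routes. The IRB table in Section 9.3 lists every death as reportable within 5 days or annually, with no 30-day limit. Section 9.1 sends all serious experiences, including fatal ones, to the supplier, and Section 9.1.2 allows no exclusions. Section 9.3 defines adverse events as occurring during or after treatment. The off-study form shows that some later information is expected. These routes exist, but they pass on deaths that someone already knows about. They oblige nobody to look, and they give no last-known-alive dates for survivors.

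A second objection is that no section says survival will be censored at progression; censoring at the date last known alive fits Section 10.1 equally well. That stands. The figures above describe the case in which nothing is recorded after progression, and partial capture is not quantified.

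Third, the 24-36-month rows make the monthly death hazard about 4 to 14 times higher after progression than before (0.0193/0.005 to 0.0289/0.002), which no document figure supports. Section 4.1 describes a chronic relapsing disease, so the 60-96-month cases may be as plausible. On the other side, Section 3.1 admits relapsed mantle cell lymphoma and up to four prior regimens. The death counts also assume 33 patients with 36 full months each. If accrual stops at 17, the 6.5-13.5 deaths scale by 17/33 to about 3.3-7.0.

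Finally, overall survival is descriptive here and drives no decision. That limits the weight of the point but does not remove the contradiction.

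**Conclusion.** The concern holds. Section 4.5 does not support the survival estimate that Sections 1.1 and 10.1 promise, and no other section fills the gap. This follows from the text and needs no assumed rates.

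The size cannot be fixed from the documents. If progressors are censored at progression, the 3-year overstatement ranges from 2.5 to 37.0 points across all the cases above, depending mainly on how long patients live after progression. It is smaller at earlier horizons, and zero if the death hazard is the same before and after progression. Even in the mildest 3-year case shown, about 45% of deaths are missed (100 − 54.9).

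This should be corrected, but it does not threaten the primary conclusion: the response analysis and stopping rule stand as designed.

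**What to change.** Amend Section 4.5 along these lines: *All treated patients, including those removed for toxicity, are followed for progression until progression or death, and for survival by chart review or telephone about every six months until death or study close.* Define study close. Six months is a practical choice; another regular interval would serve.

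Add to Section 10.1: *Patients not known to have died are censored for overall survival at the date last known alive; progression is not a censoring event.* State the start date as well.

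Apply this to patients who have already progressed. Section 4.3.8 shows that participants are already on study, and their vital status may still be recoverable. Check first that consent covers contact after leaving the study; the consent pages are not in the public file.

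The cost is at most 33 patients checked about twice a year, recorded on the existing off-study form. The sample size of 17 to 33 and the response rule do not change.

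If contact after progression is not wanted, remove survival from Objective 1.1 and Section 10.1 and report progression-free survival, with progression or death as the event. That costs only wording, but gives up overall survival as a reported outcome. Progression follow-up for patients removed for toxicity would still need to be made explicit.

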5. DOSING DELAYS/DOSE MODIFICATIONS

5.1 Vorinostat Dose Reductions for Toxicity:

Treatment will be administered at 100 mg daily less than their previous dose for patients who present to treatment and are found to have $ANC \geq 500$, but ≤ 1000 , or platelet counts $\geq 50K$ but $\leq 75K$. This dose reduction is reversible with normalization of counts.

Treatment will be held for patients who present with:

1. non-hematologic toxicity of grade 3 or 4, until toxicity resolves to below grade 2. These patients will restart at 100 mg daily less than their previous dose. If this dose leads to recurrence of the toxicity at grade 3 or greater, the patient will come off study.
2. hematologic toxicity of ANC <500, or platelet count <50K. Should dose need to be held for greater than two weeks, upon recovery of ANC >1000 or platelet count >50 patient may restart at 100 mg daily less than their previous dose. If this dose also leads to ANC<500 or platelet count <50, then patient should come off study.

Treatment will be discontinued in patients who experience toxicity of grade 3 or greater that does not resolve within 3 weeks. Requirement for more than two dose reductions mandates removal from the study. Delay of protocol treatment for more than four weeks from date of scheduled treatment mandates removal from protocol treatment, unless there are extenuating circumstances and approved by the principal investigator.

Lovenox Dose Reductions for Toxicity:

Hematologic Toxicity: If platelet count drops to <50K, lovenox should be held until platelets recover.

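### Section 5.1, item 2 joins its restart counts with 'or', so after a fall in both counts one recovery meets the restart wording while the other count still requires a hold

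*Combined protocol and SAP*

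**What the plan says.** All the relevant rules are in section 5.1 of the protocol.

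- **Hold.** "Treatment will be held for patients who present with" one of two listed conditions; the second is "hematologic toxicity of ANC <500, or platelet count <50K". Either count alone is enough.
- **Restart.** For holds longer than two weeks: "upon recovery of ANC >1000 or platelet count >50 patient may restart at 100 mg daily less than their previous dose". The platelet figure lacks its K.
- **Further fall.** "If this dose also leads to ANC<500 or platelet count <50, then patient should come off study". The K is missing here too.
- **Intermediate counts.** When ANC is 500 to 1000 or platelets are 50K to 75K, the rule is a lower dose, not a hold: "Treatment will be administered at 100 mg daily less than their previous dose for patients who present to treatment and are found to have" counts in these ranges.
- **Time limits.** "Treatment will be discontinued in patients who experience toxicity of grade 3 or greater that does not resolve within 3 weeks". A second limit concerns lateness: "Delay of protocol treatment for more than four weeks from date of scheduled treatment mandates removal from protocol treatment". The principal investigator may approve an exception to this second limit.
- **Anticoagulant.** Lovenox is held while platelets are below 50K.

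No other part of the protocol gives a hematologic restart count. Section 5.2 deals with logistical delays and unrelated illness and sets no counts.

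**The concern.** In the hold sentence 'or' is right, because either low count is a reason to stop. In the restart sentence the same 'or' lets either recovered count release the patient. That is harmless when only one count fell and the other stayed out of the hold range. It is not harmless when both fell, or when the second falls during the hold: the restart sentence is then satisfied by one count while the other still meets the hold criterion a line earlier.

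What is at stake is dosing safety. Followed literally, the restart sentence lets a site resume vorinostat with platelets below 50K or ANC below 500. The study calendar schedules a blood count once per 21-day cycle, so a wrong restart might not be picked up quickly.

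**Working it through.** The plan gives no figure to reproduce, so the check applies the hold and restart rules to the same counts and looks for combinations that satisfy both.

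**Inputs (section 5.1).** Hold if ANC <500 or platelets <50K. Restart if ANC >1000 or platelets >50, read as 50K.

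**States.** Three ANC bands × two platelet bands = 6 states at the restart decision. If both counts caused the hold:

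| ANC | Platelets | Hold criterion present | Restart wording met |
|---|---|---|---|
| <500 | <50K | yes | no |
| <500 | >50K | yes | **yes (conflict)** |
| 500–1000 | <50K | yes | no |
| 500–1000 | >50K | no | yes |
| >1000 | <50K | yes | **yes (conflict)** |
| >1000 | >50K | no | yes |

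Restart is permitted in 4 of 6 states, and 2 of those 4 still carry a hold criterion. Of the other two, one is full recovery. The other (ANC 500–1000, platelets >50K) has no hold criterion.

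**All triggers.** The hold may have been caused by ANC only, platelets only, or both: 3 × 6 = 18 cases. Entries are restarts permitted / conflicts.

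| Reading of the restart rule | ANC only | Platelets only | Both | Total |
|---|---|---|---|---|
| Current text, where a triggering count must recover and either suffices if both fell | 2/1 | 3/1 | 4/2 | 9/4 |
| Current text, literal 'or' whatever the trigger | 4/2 | 4/2 | 4/2 | 12/6 |
| Plain 'and' | 1/0 | 1/0 | 1/0 | 3/0 |
| Proposed wording (see the fix) | 1/0 | 2/0 | 1/0 | 4/0 |

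The favourable reading in the first row therefore does not remove the problem. It leaves one conflict for each single trigger, where the second count fell during the hold, and two when both fell. Treating platelets of exactly 50K as a third band (27 cases) gives totals of 11/4, 15/6, 3/0 and 5/0, so the conflict counts do not change.

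Plain 'and' also clears the conflicts, but it blocks restart after a platelet-only hold when ANC is 500–1000, where the first paragraph of 5.1 allows reduced dosing.

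**Time window.** The restart sentence applies after day 14 of a hold. The limits below assume that the toxicity and the hold both begin on the scheduled treatment date.

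- *ANC lagging:* the adverse event table in section 6.1 ties grade 3 or 4 neutrophils to ANC below 1.0 × 10⁹/L. ANC <500 therefore falls under the 3-week rule, which closes the window at about day 21.
- *Platelets lagging:* the protocol prints no platelet grade cut-off. If the 3-week rule covers platelets <50K, the window again closes at about day 21. If it does not, the limit is about day 28, or later with the principal investigator's approval.

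**The case against.** The strongest reply is that item 2, read whole, already gives the safe answer. The hold is mandatory and the restart only permissive, so a patient with ANC 1200 and platelets 40K stays on hold. 'Recovery' presupposes a fall, so 'or' naturally means whichever count fell. Most clinicians would act that way. But the text never ranks the two sentences, and the trigger-specific reading does not say that both counts must recover when both fell. It also fails when the second count falls during the hold.

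The narrow scope is a fair point and stands. The conflict needs a hold beyond two weeks, one count recovered and the other still below its hold limit. Section 2.3.4 describes thrombocytopenia as quickly reversible once the drug is interrupted, so such holds may be few. The state counts describe wording, not risk.

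The other safeguards help only in part. The 3-week rule cannot prevent a wrong restart between days 14 and 21, the 4-week rule has an exception, and the Lovenox hold stops only Lovenox. Removal after a further low count acts only once the patient has been re-exposed.

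**Conclusion.** The concern holds. Section 5.1, item 2 contains a restart condition that can be met while its own hold condition is still present: in 2 of the 4 states where restart is permitted after a two-count hold, and in 4 of 18 trigger-by-state cases even on the favourable reading. This rests on reading '>50' as 50K and on the absence of any text ranking the hold above the restart.

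The practical weight is modest. The frequency cannot be derived from the documents and is probably low, and the window is about one to two weeks unless the investigator extends it. Neither the response-rate analysis nor the two-stage design is affected. It still deserves correction, because a dosing-safety rule should not depend on readers overriding its literal wording.

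**What to change.** Replace the restart condition in section 5.1, item 2 with wording to this effect:

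> After a hold of more than two weeks, vorinostat may resume at a daily dose 100 mg lower once every count that triggered the hold has recovered (ANC >1000; platelets >50K) and neither hold criterion (ANC <500 or platelets <50K) is present.

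Add the missing K to the platelet limit in the off-study sentence that follows.

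This removes all the conflicts and keeps restart open after a platelet-only hold with ANC 500–1000. Across the 18 cases, permitted restarts fall from 9 to 4. Four of the five removed are the conflicts. The fifth is the two-count hold with platelets recovered and ANC 500–1000, which would now wait for ANC >1000.

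The cost is one reworded sentence and one unit correction, with no change to sample size or analysis. A few patients with both counts affected may restart later, and some of them could reach the 3- or 4-week removal limits. The change does not address holds of two weeks or less, for which item 2 states no restart count.
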